10.5 Analysis Populations

10.5.1 PK Analysis Population

The PP Population will serve as the primary population for the analyses of PK data in this study. The PP population consists of the subset of participants who comply with the protocol sufficiently to ensure that their PK data will be likely to exhibit the effects of treatment, according to the underlying scientific model. Compliance covers such considerations as exposure to treatment (participants' dosing compliance should be such that their PK is expected to be at steady state at the time of Week 4 assessment), availability of measurements, and absence of major protocol deviations that may affect achievement of steady state at the time of Week 4 assessment. Major protocol deviations will be identified to the extent possible prior to final database lock. Any participants or data values excluded from analysis will be identified, along with their reason for exclusion, in the CSR. At the end of the trial, all participants who are compliant with the trial procedures as aforementioned and have available data at the Week 4 PK visit will be included in the PP population.

10.5.2 Efficacy Analysis Populations

The FAS population will serve as the primary population for the analysis of efficacy data in this study. The FAS population consists of all allocated participants who receive at least one dose of study treatment.

The mFAS will be used for supportive analysis of the efficacy endpoints of SVR₁₂ and SVR₂₄. The mFAS population is a subset of the FAS population, with participants excluded for study discontinuation for reasons unrelated to the treatment regimen. Examples include loss to follow-up, discontinuation from the study due to non-drug-related AEs, informed consent withdrawal, and other non-virologic failures.

The final determination on the exclusion of participants from an analysis population will be made prior to the final database lock and will be documented in a separate memo. Details on the approach to handling missing data are provided in Section 10.6, Statistical Methods.

10.5.3 Safety Analysis Populations

The APaT population will be used for the analysis of safety data in this study. The APaT population consists of all allocated participants who received at least one dose of study

treatment. The safety analyses will include all participants who receive any dose of active treatment, but participants who receive different doses will be reported separately.

At least one laboratory or vital sign measurement obtained subsequent to at least one dose of study treatment is required for inclusion in the analysis of each specific parameter. To assess change from baseline, a baseline measurement is also required.

Details on the approach to handling missing data for safety analyses are provided in Section 10.6, Statistical Methods.

10.6 Statistical Methods

This section describes the statistical methods that address the primary and secondary objectives. Methods related to exploratory objectives will be described in the sSAP.

10.6.1 Statistical Methods for Pharmacokinetic Analyses

Each NCA PK parameter of interest (AUC_{0-24} , C_{max} , C_{trough} , and CL/F) of EBR and GZR at Week 4 will be summarized separately by Age Cohort and treatment as appropriate, with GMs and 95% CIs based on natural log-transformed analysis and t distribution.

Individual values will also be listed for each PK parameter at Week 4 by Age Cohort and dose level as appropriate, and the following (non-model-based) descriptive statistics will be provided: N (number of participants with non-missing data), arithmetic mean, standard deviation, arithmetic percent coefficient of variation (CV) (calculated as $100 \times$ standard deviation/arithmetic mean), median, minimum, maximum, GM, and geometric percent CV (calculated as $100 \times \sqrt{exp(s2) - 1}$, where $s2$ is the observed variance on the natural log-scale). Descriptive statistics will also be provided for concentrations/PK parameters obtained at other time points, as appropriate.

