5.1 Overall Design

This is a non-randomized, single arm, multiple cohort, multi-site, open-label Phase IIb trial of EBR/GZR in pediatric participants aged 3 to less than 18 years with chronic HCV infection GT1b/1-other; GT1a without baseline NS5A RAS at positions 28, 30, 31, and/or 93; or GT4, to be conducted in conformance with Good Clinical Practice.

The goals of this Phase IIb trial are: 1) to define doses for EBR/GZR in children by assessing plasma PK concentrations that target a similar PK to that seen in adults receiving EBR 50 mg and GZR 100 mg. The PK target has been defined by the clinical PK comparability bounds, within which there were no clinically important differences for safety and efficacy; 2) to establish the tolerability, safety, and efficacy of the combination therapy in the pediatric HCV-infected population. All participants will receive EBR/GZR without RBV for 12 weeks.

The trial will enroll participants into three Age Cohorts:

1. Age Cohort 1 (aged 12 years to less than 18 years)
2. Age Cohort 2 (aged 7 years to less than 12 years)
3. Age Cohort 3 (aged 3 years to less than 7 years)

Each Age Cohort starts with a Mini Age Cohort of 7 participants before enrolling additional participants into the Expanded Age Cohort. The enrollment requirements for the Mini and Expanded Age Cohorts are shown in [Table 2](#).

Table 2 Enrollment Requirements for Each Age Cohort

Age Cohort	Age Range	Enrollment Requirements	
		Mini Cohort	Expanded Cohort
1	12 to <18 years	
 • N=7 (to ensure at least 6 participants with evaluable PK) • At least 2 participants aged <14 years 	
 • N=~15 • At least 3 participants aged 12 to <14 years • At least 3 participants aged 16 to <18 years
2	7 to <12 years	
 • N=7 (to ensure at least 6 participants with evaluable PK) • At least 2 participants aged <9 years 	
 • N=~20 • At least 5 participants aged 7 to <12 years • At least 5 participants aged 3 to <7 years 
 ○ At least 2 participants aged <5 years
3	3 to <7 years	
 • N=7 (to ensure at least 6 participants with evaluable PK) • At least 2 participants aged <5 years 	

The enrollment of participants will occur as follows:

1. Mini cohorts of the two oldest Age Cohorts will enroll in the first wave of participants.
 - a. Mini Age Cohort 1
 - b. Mini Age Cohort 2

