Enrollment into Mini Age Cohort 2 will follow Mini Age Cohort 1 by 2 to 3 weeks to allow time to review Day 1 PK (AUC) in a minimum of 6 participants of Mini Age Cohort 1 before enrolling Mini Age Cohort 2. The Week 4 intensive PK from the first two Mini Age Cohorts (N=~14), in addition to the Day 1 and Week 8 sparse PK, will be used to update the population PK and PBPK models to select optimal doses for Mini Age Cohort 3 and Expanded Age Cohort 1.

2. Mini Age Cohort 3 and Expanded Age Cohort 1 will enroll in the second wave of participants after optimal doses have been selected based on PK modeling results from the first wave of participants.
 - a. Expanded Age Cohort 1 will enroll following completion of the PK modeling analyses; dosing will use the proposed dose for each component, EBR and GZR, and dose recommendation by weight bands will be used.
 - b. Mini Age Cohort 3: PK modeling and simulation will be used to propose dosing for each component, EBR and GZR. Dose recommendation by weight bands will be used for Mini Age Cohort 3.

Data from the three Mini Age Cohorts and from Expanded Age Cohort 1 will be used to update the population PK and PBPK models in order to propose doses for Expanded Age Cohorts 2 and 3.

3. Expanded Age Cohorts 2 and 3 (Expanded Age Cohort 2/3)

- a. Expanded Age Cohorts 2 and 3 are combined as a single group Age Cohort 2/3. This age cohort will enroll following completion of the updated PK modeling analyses that incorporates PK data from all previous cohorts, including all 21 participants from the three Mini Age Cohorts and all 15 participants from Expanded Age Cohort 1. Dosing of Expanded Age Cohort 2/3 will use the modeling and simulation proposed dose for each component, EBR and GZR.

While age cohorts are used for the purposes of enrollment, dose recommendations by weight bands will be used for Mini Age Cohort 3 and the Expanded Age Cohorts. Weight bands will be determined based on the PK analyses.

Following the conclusion of this study and the Clinical Study Report (CSR) for the study, a final PK model will be developed that includes all PK data from participants aged 3 years up to 18 years, in addition to relevant adult data previously collected in the program. The final model and proposed pediatric dosing regimen will be summarized in a separate report.

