7.1 Treatments Administered

The study treatments to be used in this trial are outlined below in [Table 5](#).

Table 5 Study Treatments

Study Treatment Name:	EBR/GZR FDC	Placebo to match MK-5172A (EBR/GZR) FDC*	MK-8742 (EBR) Pediatric Formulation	MK-5172 (GZR) Pediatric Formulation
Dosage Formulation:	Tablet	Tablet	Oral granules***	Oral granules***
Unit Dose Strength(s):	50 mg/100 mg	0 mg/0 mg	0.5 mg	1 mg
Dosage Level(s):	1 tablet QD	1 tablet given prior to allocation**	TBD – dose will not exceed 50 mg	TBD – dose will not exceed 100 mg
Route of Administration:	Oral	Oral	Oral	Oral
Sourcing:	Sponsor	Sponsor	Sponsor	Sponsor

*Placebo tablets are different in color but identical in size and shape to the active EBR/GZR FDC tablets.

**Placebo to EBR/GZR (FDC) tablet is given once prior to allocation to participants in Mini Age Cohort 1. This will also apply to participants in Expanded Age Cohort 1 if it is determined by PK analysis that Expanded Age Cohort 1 will also receive the adult FDC dose.

***Pediatric formulation supplied as single entity packets.

EBR = elbasvir; FDC = fixed dose combination; GZR = grazoprevir; PK = pharmacokinetics; QD = once-daily; TBD = to be determined.

As PK data becomes available, the dose proposed for participants will be adjusted to meet the scientific goals and study objectives.

Mini Age Cohort 1 will be administered FDC tablets (EBR 50 mg/GZR 100 mg). Expanded Age Cohort 1 is expected to receive FDC tablets but alternatively may receive pediatric formulation, if PK data suggests a lower dose (dosage to be informed by trial). Age Cohorts 2 and 3 will be administered pediatric formulation product (dosage to be informed by trial). Following assignment of formulation, participants may not change from FDC tablets to pediatric formulation or from pediatric formulation to FDC tablets during the course of the trial.

The pediatric formulation in this study allows for flexibility of dosing. EBR 0.5 mg and GZR 1.0 mg are packaged as single entity packets, which contain oral granules. The foil packets are opened and the contents (oral granules) are mixed into a soft food vehicle (applesauce, pudding, or yogurt) prior to consumption.

Each single entity packet is individually labeled with the Sponsor's product number (MK-8742 is EBR; MK-5172 is GZR) and contains 10 oral granules of either EBR or GZR.

- EBR packets have 5 mg per unit package and
- GZR packets have 10 mg per unit package

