The recommended dosing for each Age Cohort will be detailed by the Sponsor in a memo to the Study File. Dosing recommendations for Mini Age Cohort 3 and all Expanded Age Cohort(s) will be by weight bands, which will be determined based on PK analyses. This memo will be communicated to the site personnel. The memo should be forwarded to the Institutional Review Board/Ethics Review Committee (IRB/ERC) by the Investigator, as appropriate per IRB/ERC guidelines.

All placebos were created by the Sponsor to match the active product.

All supplies indicated in [Table 5](#) will be provided per the ‘Sourcing’ row depending upon local country operational requirements. Every attempt should be made to source these supplies from a single lot/batch number. The trial site is responsible for recording the lot number, manufacturer, and expiry date for any locally purchased product as per local guidelines unless otherwise instructed by the Sponsor.

Refer to section 9.1.8 for details regarding administration of the study treatment.

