10.1 Statistical Analysis Plan Summary

Key elements of the Statistical Analysis Plan (SAP) are summarized below; the comprehensive plan is provided in Sections 10.2 to 10.12.

Study Design Overview	A Phase IIb Study to Assess the Pharmacokinetics, Safety, and Efficacy of the Combination Regimen of Elbasvir (EBR)/Grazoprevir (GZR) in Pediatric Participants Aged 3 to Less Than 18 Years with Chronic Hepatitis C Infection
Treatment Assignment	This will be an open-label, non-randomized trial. Participants infected with HCV GT1a without baseline NS5A RASs at position 28, 30, 31, and/or 93; GT1b/1-other; or GT4 with HCV RNA <800,000 IU/mL; TN or PR TE (GT1 only); cirrhotic or NC, will be treated with EBR/GZR for 12 weeks within Age Cohorts (12 to <18 years, 7 to <12 years, and 3 to <7 years). Approximately 22 participants in the oldest cohort (12 to <18 years) will be enrolled. Approximately 34 participants will be enrolled in the two younger cohorts, with 12 to 22 participants in each. The total number of participants enrolled in the three cohorts will be ~56.
Analysis Populations	PK: Per-Protocol (PP) Safety: All Participants as Treated (APaT) Efficacy: Full Analysis Set (FAS) and modified FAS (mFAS)
Primary Endpoints	AUC ₀₋₂₄ , C _{max} , C _{trough} , and CL/F of EBR and GZR.
Secondary Endpoints	1. Number of participants experiencing AEs and discontinuing study drug due to AEs. 2. SVR ₁₂ (Sustained Virologic Response 12 weeks after the end of all study therapy), defined as HCV RNA <LLOQ (either TD[u] or TND) 12 weeks after the end of all study therapy.
Statistical Methods for Key Pharmacokinetic and Efficacy Analyses	Geometric means and 95% confidence intervals (CIs) will be provided for AUC ₀₋₂₄ , C _{max} , and CL/F of EBR and GZR by age cohort and dose level. The proportion of participants achieving SVR ₁₂ will be estimated using a 95% CI (via the Clopper-Pearson method). The missing data approach will be Missing=Failure (M=F).
Statistical Methods for Key Safety Analyses	Safety and tolerability will be assessed by clinical review of all relevant parameters including AEs and laboratory tests. Descriptive statistics will be provided for these safety parameters.
Interim Analyses	Periodic safety analyses will be conducted for the accruing data and will be reviewed by an eDMC at regular intervals as outlined in the eDMC charter. This will supplement routine in house medical monitoring.

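### Should the Week 4 PK summary be pooled by weight band, given that most children are dosed by weight band and not by age?

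*Combined protocol and SAP*

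**What the plan says.** Section 10.6.1 plans GMs and 95% CIs for Week 4 AUC0-24, Cmax, Ctrough and CL/F of both drugs. Each parameter "will be summarized separately by Age Cohort and treatment as appropriate". The same section lists individual values and gives descriptive statistics, including the GM, by Age Cohort and dose level. The SAP summary in 10.1 likewise presents GMs and CIs "of EBR and GZR by age cohort and dose level".

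Dosing is organized differently. Section 5.1 states: "While age cohorts are used for the purposes of enrollment, dose recommendations by weight bands will be used". This covers every Expanded cohort and the youngest Mini cohort. Section 7.1 repeats it: "Dosing recommendations for Mini Age Cohort 3 and all Expanded Age Cohort(s) will be by weight bands". The bands are not defined in the documents; PK analyses will set them.

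Section 5.5.1.1 applies the AUC window to the GM of each age group. In Section 10, weight bands appear in two places: model-based dose selection (10.6.2) and the SVR12 subgroups (10.10).

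**The concern.** By Table 2, 7 + about 15 + about 20 = about 42 of 56 participants belong to cohorts dosed by weight band. Yet the observed primary PK endpoint is tabulated by age. A band that spans two age cohorts would be reported in two pieces, each with a wider CI than the pooled group, and the AUC window would not be checked by band. SVR12, a secondary endpoint, does get a band-level estimate, which makes it look as though weight bands were never carried through to PK.

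If the by-age table were what supported the band doses, this would matter: the evidence would be in one unit and the recommendation in another.

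**Working it through.** **1. The plan's own precision figures.** Inputs from 10.9.1: log-scale between-subject SD 0.731 (GZR) and 0.452 (EBR), two-sided 95% CI, about 80% assurance. With a t interval on the log scale and the 80th percentile of the sample variance:

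X = 100 × [exp( t(0.975, n−1) × SD × √(χ²(0.80, n−1)/(n−1)) / √n ) − 1]

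For GZR at n = 5: t = 2.776 and χ²/(n−1) = 5.989/4 = 1.497. So X = 100 × [exp(2.776 × 0.731 × √1.497 / √5) − 1] = 203.6%; Table 12 prints 204%.

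| n | GZR computed / Table 12 | EBR computed / Table 12 |
|---|---|---|
| 5 | 203.6 / 204 | 98.7 / 99 |
| 12 | 70.9 / 71 | 39.3 / 40 |
| 15 | 58.6 / 59 | 33.0 / 33 |
| 22 | 43.6 / 44 | 25.1 / 25 |

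All agree within one percentage point, so the formula can be used for other group sizes.

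**2. What pooling could gain.** Band sizes are an assumption, because no bands are defined. Pooling also assumes the same GM at both ages for the same band and dose.

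| Split of one band over two age cells | Separate cells, GZR / EBR | Pooled, GZR / EBR |
|---|---|---|
| No band spans ages | no change | no change |
| 5 + 5 | 204% / 99% each | n = 10: 84% / 46% |
| 5 + 15 | 204% / 99% and 59% / 33% | n = 20: 47% / 27% |
| 10 + 10 | 84% / 46% each | n = 20: 47% / 27% |

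The 5 + 5 row cannot be the whole of Expanded Age Cohort 2/3. Table 2 sets its size at about 20 with two age groups. Its minimum, "At least 5 participants aged 7 to <12 years", with the same minimum for ages 3 to <7, means that if one group has 5 the other has about 20 − 5 = 15. So 5 + 5 can only be part of that cohort. The 5 + 15 and 10 + 10 rows put every child aged 3 to <12 in that cohort on one band and one dose, so there would be no banding within it. They are limits, not typical cases.

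**3. How many children could be affected.** Section 7.1 says that "Expanded Age Cohort 1 is expected to receive FDC tablets but alternatively may receive pediatric formulation", and that "Age Cohorts 2 and 3 will be administered pediatric formulation product". The tablet has one strength (50 mg/100 mg). In the expected case, Expanded Age Cohort 1 takes one dose in one formulation; its age cell is already its dose cell, and it should not be pooled with children on granules. That leaves 42 − 15 = 27 children (7 in Mini Age Cohort 3 and about 20 in Expanded Age Cohort 2/3). Of these, only children in a band that crosses age 7 and shares one dose gain anything. The figure of 42 would apply only if Expanded Age Cohort 1 moved to granules.

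**4. What supports the band doses.**
- Section 4: the primary objective is steady-state PK grouped by age. Sections 10.1, 10.6.1 and 5.5.1.1 use that grouping.
- Section 3.1: the Week 4 intensive PK updates the population PK model to support pediatric dosing recommendations.
- Section 10.6.2: doses by band are selected by population PK and PBPK modeling, updated as each cohort's data arrive. This uses data across ages.
- Section 5.1: a final model with all pediatric PK data plus relevant adult data, and the proposed regimen, go into a separate report.

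**5. Whether a band table could change a decision.** Under 5.5.1.1, a GM outside the window leads to dose adjustment for the Expanded Age Cohorts. The last group dosed is the combined one: "Expanded Age Cohorts 2 and 3 are combined as a single group Age Cohort 2/3". The banded cohorts before it are Mini Age Cohort 3 and Expanded Age Cohort 1, which have non-adjacent age ranges (3 to <7 and 12 to <18). Within Mini Age Cohort 3, dose level already separates bands on different doses, and splitting its 7 children 3 + 4 gives GZR precision of 901% and 325%, against 124% for all seven. A pooled band result from Expanded Age Cohort 2/3 would come after the last dosing step in the trial.

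**The case for a change.** The strongest argument for the table is that non-compartmental Week 4 PK is the declared primary endpoint, and an observed result beside the model-based one is a useful check in the unit of dosing. Sections 10.6.2 and 10.10 carry weight-band wording and 10.6.1 does not. The separate modeling plan is only optional. A band crossing age 7 is plausible, since Expanded Age Cohort 2/3 is one group aged 3 to <12 on one formulation. The cost is one more output per parameter.

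The factual part stands: no section plans an observed GM and CI by band pooled over ages, and the modeling does not supply one. The allowance for grouping as appropriate in 10.6.1 does not name weight bands either. But this shows that a further descriptive view is possible, not that the planned one misleads. Age-by-dose-level cells and individual listings already let a reader compare observed exposure with the model. The provision for a supplemental SAP leaves room for a band table once bands exist.

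**Conclusion.** The concern does not hold. The by-age summary and the by-age AUC window follow the primary objective, Table 12 reproduces within one percentage point, and band dosing rests on models that use all ages. Following the plan as written gives a sound result. A pooled band table would be reporting only: it would alter no dose rule, no in-trial decision and no planned estimate.

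The possible gain runs from nothing (no band crosses an age boundary) to a limit of 84% down to 47% for GZR and 46% down to 27% for EBR (10 + 10). A small age cell could gain more, from 204% to 47% for GZR in the 5 + 15 split, but that also needs all of Expanded Age Cohort 2/3 on one dose. This assumes the SDs in 10.9.1 and no age difference in GM within a band and dose. The reach of at most about 27 children assumes that Expanded Age Cohort 1 takes tablets, as the protocol expects. Presenting the table is a matter of preference.

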10.6.2 Modeling and Simulation for Dose Selection

The starting dose for Mini Age Cohort 2 may be refined, if needed, based on the descriptive PK data for Day 1 from Mini Age Cohort 1. All PK data from Mini Age Cohort 1 and Mini Age Cohort 2 will be incorporated with previous adult data into the adult population PK and PBPK models, which will be continuously updated as pediatric PK data become available from each Age Cohort. Modeling and simulation will be used to select doses for Mini Age Cohort 3 and Expanded Age Cohort 1. All PK from these cohorts will in turn be used to update the models, and select the dose for Expanded Age Cohort 2/3. Dose selection by weight bands will be used. Weight bands will be determined based on PK analyses. At each step, the goal of model-based simulations will be to derive a dosing regimen expected to provide similar exposures in pediatric patients as in adults. A separate Modeling and Simulation Analysis Plan with further details on the methodology may be prepared.

10.6.3 Statistical Methods for Efficacy Analyses

Efficacy results will be presented by Age Cohorts (12 to <18 years, 7 to <12 years, 3 to <7 years). Results of participants in the Expanded Age Cohorts will be reported separately from those in the Mini Age Cohorts, unless the same dose was given to both Mini and Expanded

Cohorts within the age group. If all participants in an Age Cohort received the same dose, then results of participants in both Mini and Expanded Age Cohorts will be reported together.

Missing Values

A missing data point for a given study visit may be due to any one of the following reasons: a visit occurred but data were not collected or were unusable; a visit did not occur; or a participant discontinued from the study before reaching the visit. Participants who prematurely discontinued the assigned treatment are encouraged to remain in the study for the follow-up, if possible.

The HCV RNA outcome is categorized as TND, TD(u), and TD(q). There are 3 types of missing data handled by different approaches.

Type 1 is intermittent missing:

- Intermittent missing: If a missing data point is immediately preceded and followed by non-missing HCV RNA outcomes, the missing value will be imputed to the worst outcome of the two. For example, if a missing data point is preceded by TD(q) and followed by TD(u) or TND, then the missing value would be imputed as TD(q); if a missing data point is preceded by TD(u) and followed by TND, then the missing value would be imputed as TD(u); when a missing value is flanked by two TND, then the missing value would be imputed as TND.

Type 2 and 3 are both non-intermittent missing, but differ regarding their relationship to the study drug:

- Type 2 -- Non-intermittent missing related to the study drug: Missing values due to premature study discontinuations with reasons related to treatment either for safety or efficacy.
- Type 3 -- Non-intermittent missing unrelated to the study drug: Missing data due to premature study discontinuations with reasons unrelated to treatment such as loss to follow-up, protocol violation, withdrawal of consent/assent, administrative reasons, etc.

The following two approaches will be used to handle non-intermittent missing data (Type 2 and 3) due to premature discontinuations, depending on the analytical strategy, as described in the section below and in [Table 10](#).

- Missing = Failure (M=F) approach: Participants with non-intermittent missing results (ie, Type 2 or Type 3 missing) will be imputed as having failed, regardless of the reason for study discontinuation.
- Treatment-Related Discontinuation = Failure (TRD=F) approach: Participants with treatment-related Type 2 missing data will be considered as having failed; whereas participants who have Type 3 missing values and have not experienced virologic failure during the observed study period will be excluded from the analysis for the time points following their study withdrawal. Participants with documented virologic failure during the treatment or follow-up period, even if they withdrew prematurely due to reasons not related to study drug, are classified as failures.

In addition, a missing baseline/Day 1 HCV RNA result will be replaced with a screening result, if available.

Proportions of Participants With Virologic Responses

For the efficacy analysis to estimate the proportion of participants achieving SVR₁₂, a 95% CI will be calculated using the Clopper-Pearson method [Clopper, C. J. and Pearson, E. S 1934]. The missing data approach of M=F described above will be utilized for the key analysis. The same method will be used to analyze all binary endpoints.

Sensitivity analyses will be performed for the primary endpoint using the mFAS population and the TRD=F missing data approach.

[Table 10](#) includes a summary of the key efficacy analyses.

Table 10 Analysis Strategy for Key Efficacy Variables

Endpoint/Variable (Description, Time point)	Primary vs Secondary Approach [†]	Statistical Method	Analysis Population	Missing Data Approach [‡]
Proportion of participants achieving SVR ₁₂	P	95% Confidence Interval (Clopper- Pearson)	FAS	M=F
Proportion of participants achieving SVR ₁₂	S	95% Confidence Interval (Clopper- Pearson)	mFAS	TRD=F

[†]P=Primary approach; S=Secondary approach.
[‡] Imputation for specific missing values described in Section 10.6.2.
FAS = Full Analysis Set; M=F = Missing = Failure; mFAS = modified Full Analysis Set; TRD=F = Treatment-Related Discontinuation = Failure.

Participant Virologic Failure: Non-Response, Rebound, Breakthrough, or Relapse

Summary statistics will be provided to describe the rates of occurrence of virologic non-response, rebound, breakthrough, or relapse. Definitions for virologic non-response, rebound, breakthrough, or relapse are in Section 5.4.2.1.1.

